## SIGNIFICANCE

Aspiration pneumonia (AP), caused by inhalation of food or liquids (aspiration) in people with oropharyngeal dysphagia (OPD), has been increasingly recognized as a significant cause of morbidity and mortality [1], raising its contribution to known overall pneumonia incidence five-fold (Figure 1) [2]. If patients with cardiovascular disease and ischemic stroke develop OPD during their illness, the chance of death can be doubled [3]. In acute care and nursing homes, where OPD has up to 75% prevalence, and for the half of the 800,000 US citizens who suffer strokes each year and develop OPD, late detection of OPD leads to AP, increasing mortality risk up to three-fold, adding nearly \$500 million to US health care costs, and causing dramatic deterioration in quality of life [4-10]. Screening for OPD in these settings, a process based on human observation of a patient swallowing (videofluoroscopy – “VF”), fails to identify many patients with silent OPD who remain unidentified until adverse events like AP occur. Thus, a quick, accurate method of predicting the presence and absence of silent and overt OPD is needed to prevent the inadvertent aspiration of food, liquids and colonized oral secretions that lead to pneumonia. We are developing such an instrumental screening tool, the **Aspirometer**, which, when deployed at the time of admission or first suspicion of a disease that causes OPD, can identify OPD early, and prevent the consequences of silent OPD.

[figure not shown]
**Scientific Premise:** OPD is caused by disease-related disruptions in swallowing kinematics (e.g., timely and complete movement of oropharyngeal structures) or swallow physiology (force and symmetry of muscular contractions, neuromuscular transmission, sensory function). These impairments lead to outcomes such as airway penetration and aspiration, and excessive amounts of post-swallow oral or pharyngeal residue that are aspirated. OPD patients are suspected of aspirating when they cough or choke while eating or drinking or fail a screening test. They are then referred for diagnostic testing with VF which is the gold standard for characterizing silent aspiration and OPD. VF is never used for screening because it requires trained personnel to perform and interpret [13] and would add costs of over \$320 million annually to screen just people with stroke. Many people who aspirate do not have reflexive airway protective responses to aspiration and do not cough or choke rendering this “silent aspiration” undetectable at the bedside, hence many patients develop aspiration pneumonia [11, 12] before its risk is known.

A major gap exists between the convenience, low cost and imprecision of screening, and the sophistication, expense, precision and preventive benefits of VF. Inexpensive and convenient bedside standard institutional

**Figure 2 –** Comparing the current practices with data analytics of HRCA. Forms and patient observations are currently used by clinicians to subjectively judge the presence of dysphagia. The Aspirometer can provide an objective dysphagia assessment approach.

and in up to 50% of thicker liquid aspiration events among people with Parkinson’s disease [18]. Moreover, judgments of wet voice are misleading and poor indicators of aspiration or dysphagia [17], exhibit poor sensitivity and inter-judge reliability [19], and even using acoustic analysis of voice production parameters to assess voice after swallows cannot reliably predict airway penetration [20]. Aside from their previously

**Figure 1 –** Increased pneumonia (22.6%) vs aspiration pneumonia (93.5%) incidence 1991-1998.

increased pneumonia without the use of instrumentation

aspiration pneumonia who remain unidentified until adverse events like AP occur. Thus, a quick, accurate method of predicting the presence and absence of silent and overt OPD is needed to prevent the inadvertent aspiration of food, liquids and colonized oral secretions that lead to pneumonia. We are developing such an instrumental screening tool, the **Aspirometer**, which, when deployed at the time of admission or first suspicion of a disease that causes OPD, can identify OPD early, and prevent the consequences of silent OPD.

**Scientific Premise:** OPD is caused by disease-related disruptions in swallowing kinematics (e.g., timely and complete movement of oropharyngeal structures) or swallow physiology (force and symmetry of muscular contractions, neuromuscular transmission, sensory function). These impairments lead to outcomes such as airway penetration and aspiration, and excessive amounts of post-swallow oral or pharyngeal residue that are aspirated. OPD patients are suspected of aspirating when they cough or choke while eating or drinking or fail a screening test. They are then referred for diagnostic testing with VF which is the gold standard for characterizing silent aspiration and OPD. VF is never used for screening because it requires trained personnel to perform and interpret [13] and would add costs of over \$320 million annually to screen just people with stroke. Many people who aspirate do not have reflexive airway protective responses to aspiration and do not cough or choke rendering this “silent aspiration” undetectable at the bedside, hence many patients develop aspiration pneumonia [11, 12] before its risk is known.

A major gap exists between the convenience, low cost and imprecision of screening, and the sophistication, expense, precision and preventive benefits of VF. Inexpensive and convenient bedside standard institutional

screening (SIS) protocols for OPD are present in many settings [14, 15]. Published, validated SIS’s [21-23] are based on human observations of patients swallowing water, observing for signs of OPD using standard procedures (Figure 2). SIS performed by ordinary observers (nurses, nursing assistants) relies on whether the patient coughs or chokes during or after swallowing to predict aspiration (Figure 3). Patients who “fail” SIS all receive interventions to mitigate pneumonia risk including gold standard testing using VF, to guide these interventions, whether or not they have OPD. Patients who “pass” SIS (no coughing or choking) either do not aspirate, or they have undetected silent aspiration (which occurs in up to 40% of aspirators), and resume unsafe oral intake without intervention [16]. Popular, but weak, SIS signs of aspiration such as “wet voice quality” after swallowing, have not proven sufficiently reliable as valid predictors of aspiration [17]. A “wet voice” is absent in up to 80% of thin-liquid aspiration events,

described weaknesses, adherence to the screens' protocols varies [5, 24], reducing the validity and precision of SIS. **No currently available SIS can identify silent aspiration or OPD-related** risk of pneumonia, malnutrition, and dehydration [25, 26]. Thus, an inexpensive and accurate silent aspiration detection tool is needed and our research has produced strong lines of evidence toward that end. Our scientific premise is that the Aspirometer, an accurate, early-warning, easy to use, noninvasive tool to detect silent aspiration and OPD, can lead to pre-emptive identification of silent aspirators and significantly reduce morbidity, mortality, and health care expenditures.

"Cervical auscultation" (CA) methods rely on use of a stethoscope (Figure 2) to listen to and subjectively interpret the sounds emanating from the throat during a swallow. Limited by the narrow detection capacity of the human auditory system and limited signal transmission by the stethoscope, research has repeatedly confirmed CA's poor accuracy and reproducibility, and poor inter-examiner agreement as to the kinematic impairments producing the sounds observed, leaving its ability to identify at-risk patients with silent aspiration poor [27, 28]. Our previous work has shown promising results toward improving the objectivity and accuracy of CA [29-31], with high resolution instrumentation that can record the entire digital spectrum of these swallowing sounds that analog methods with stethoscopes and the human auditory system cannot transmit, perceive and process. The **Aspirometer**, relies on high resolution cervical auscultation (HRCA) that records swallowing vibrations and sounds with miniaturized high-resolution triaxial accelerometers and microphones placed over the anterior throat (Figure 2). Signals are then analyzed objectively with advanced data analytics far exceeding the abilities of stethoscope-human judgment.

[figure not shown]
The central challenge to deployment of the Aspirometer is that our current methods have been developed only with 274 patients with suspected OPD. Our preliminary results (see A1.c and A2.c) have shown that our algorithms have become increasingly accurate at identifying HRCA signals that correspond to many swallow kinematic events contributing to OPD and airway protection during swallowing [32-36]. To define

the entire dysphagia severity continuum and a cutoff for silent OPD presence, we need to complete the severity continuum by analyzing swallows from completely healthy control participants and compare them to impaired swallows in patients with dysphagia including those with silent aspiration. Our overall hypothesis, formed on our strong preliminary results (see **Approach**), is that the HRCA-based screening can independently and accurately predict silent aspiration and OPD before it can cause harm in patients with OPD. Based

on our strong preliminary data, we expect that HRCA-based screening with the Aspirometer will identify pneumonia risk earlier in people with new diagnoses that cause OPD and silent aspiration by detecting significantly more patients with clinically significant OPD than SIS alone, and identify those who fail screens but do not have OPD (Figure 4). The proposed approach will lead to HRCA-based characterization of the entire continuum of healthy and disordered swallow function, equation of this HRCA continuum with established measures of OPD severity, and development of the Aspirometer as a reliable dysphagia screening tool that can be implemented immediately upon the first suspicion that a patient has suspected OPD, regardless of the setting. This will lead to pre-emptive prevention of healthcare associated, hospital and community acquired OPD-related pneumonias and other OPD-related adverse outcomes.

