## SPECIFIC AIMS

Hundreds of thousands of people annually suffer from compromised nutrition, hydration, and quality of life due to impaired swallowing (oropharyngeal dysphagia or OPD), and aspiration of swallowed food into the respiratory system. OPD leads to aspiration pneumonia (AP) which increases the risk of death during hospitalization threefold, and adds 53,000 annual hospitalization days and nearly \$550 million to US health care costs annually. Through our research, we seek to pre-emptively prevent OPD diagnoses from evolving into aspiration pneumonia, and mitigate these economic and human costs. Gold-standard videofluoroscopy (VF), used to objectively diagnose OPD, is not an appropriate screening tool due to its invasiveness, size and prohibitive cost, and it cannot be deployed immediately upon suspicion of OPD. Standard institutional screening (SIS) protocols are therefore used to predict OPD. But since they rely solely on subjective, non-instrumented human judgment of OPD risk by simply watching the patient swallowing and observing for choking, a) their sensitivity is compromised because half of aspirators do not choke due to silent aspiration, b) their specificity is compromised because up to 60% of nonaspirators cough during SIS, and c) in settings in which subsequent VF is not available or feasible, SIS provide no diagnostic information to guide intervention because they cannot identify the swallowing impairments leading to aspiration.

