**Table 3 – Sensitivity and specificity of screening protocols for aspiration.**  
SENS = Sensitivity; SPEC = Specificity; FPR = False Positive Rate; FNR = False Negative Rate.

Test	SENS	SPEC	FPR	FNR
Volume-Viscosity Screening Test	100%	29%	72%	0%
Daniels Swallow Screen	92%	66%	33%	8%
Gugging Swallow Screen	100%	50%	50%	0%
Yale Swallow Protocol	100%	44-64%	36-56%	0%

classified) and specificity (the percentage of patients without an underlying problem, who are correctly classified). When compared to blinded ratings of nonconcurrent instrumental exams, swallow screenings err on the side of over-identifying aspiration risk, i.e., good sensitivity but poor specificity (see Table 3). While it may be argued that this bias in favor of sensitivity constitutes a conservative “safety net” for finding swallowing difficulties, it also results in unnecessary interventions for patients without significant OPD (Figure 3) including withholding oral dietary intake and diet texture restrictions, placement of feeding tubes, and unnecessary referrals for costly assessments, all of which affect quality of life and place financial and other burdens. A screening protocol should be performed in ordinary settings by typical screening staff, and detect OPD accurately while incurring minimum risk for the patient. Our approach to this aim will produce results that can demonstrate superior identification of both people with and without OPD compared to prior OPD screening research which exhibits zero identification of silent aspiration and only about 60% identification of those without OPD.

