### **A3.d. Experimental approach:** The main goal of this aim is to demonstrate that the proposed HRCA tool is objective and can improve upon the accuracy of SIS alone in identifying participants who have OPD and need to undergo a VF exam or need immediate intervention (Figure 11). To achieve this goal, we will carry out the following experimental steps:

STEP 1: Enroll 50 consenting patients eligible for SIS in the experiment, and perform combined SIS screening and an HRCA screening. STEP 2: The HRCA system will be applied to all patients. The dysphagia SIS screen employed in the University of Pittsburgh Medical Center Presbyterian University Hospital will be performed, which consists of two or three 5mL water swallows and drinking 90mL of water at a self-selected pace. STEP 3: Nurses or other staff (non-SLPs or physicians) administering the screens and blinded to the HRCA output, will score the screens on the basis of the institutional SIS algorithm, denoting any signs of OPD or penetration/aspiration (e.g., wet voice, coughs) for each swallow that is observed. For the concurrent HRCA screening, we will record and denote the output of the algorithm for each observed swallow with findings from Aims 1 & 2. STEP 4: We will administer a VF exam for all patients using clinical protocols that include the same bolus conditions (5mL thin liquid, 30mL thin liquid) of swallowed material used in the SIS, within a 24-hour period to confirm the presence or absence of dysphagia/aspiration. STEP 5: The MBSImP, the PAS and the Normalized Residue Ratio Scale will be used to measure swallow impairment, airway protection and post-swallow pharyngeal residue. These measures will be made by our trained laboratory associates. STEP 6: HRCA, SIS, and VF results will be compared.

**Table 4 –** HRCA-based screening can detect aspiration, validated against concurrent VF. SENS = Sensitivity; SPEC = Specificity; FPR = False Positive Rate; FNR = False Negative Rate; PB = Per bolus; PP = Per participant.

Parameter	Statistic	PB	PP
Impaired Swallowing Safety (13/40 patients; 55/154 swallows)	SENS	90%	100%
	SPEC	77%	54%
	FPR	23%	48%
	FNR	10%	0%

**Figure 12 –** Our proposed experimental and data analysis approach for Aim 3.

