**A3.e. Data interpretation:** We will fit a series of logistic regression models with presence/absence of clinically significant OPD/aspiration as the dichotomous dependent variable, and HRCA signatures and SIS, both individually and in combination, as the independent variables. We will use areas under ROC curves (c-statistics) as measures of predictive accuracy, and compare them using DeLong's method [133]. We anticipate that the c-statistics for the 3 models involving HRCA will be significantly greater than that using SIS alone.

**A3.f. Expected outcomes:** The benchmark for success of Aim 3 will be a successful completion of proposed testing of the HRCA-based screening in a clinical setting yielding accurate identifications of patients at risk of silent aspiration. Specifically, we will: (1) test the HRCA-based screening in clinical settings and denote its accuracy; (2) understand if confounding clinical factors can affect the deployment of the HRCA-based screening (not expected from our preliminary work). Successful completion of this aim will demonstrate that the Aspirometer (HRCA and advanced data analytics) can conveniently, noninvasively, and inexpensively produce robust predictions of OPD presence and absence that are measurably superior to SIS, and produce some diagnostic results currently possible only with VF testing.

**A3.g. Challenges and contingency plans:** The preliminary results (see A3.c.) strongly support our hypothesis (see A3.a.). In the highly unlikely event that our judges' PA or MBSImP score ratings drift unacceptably, we will increase surveillance on inter- and intra-rater reliability and pull judges from analysis and retrain them to criterion, retest their reliability before placing them back online.

**A3.h. Sample size justification:** We plan to recruit 50 patients, with an anticipated effective sample size of 46 after refusals. Assuming that approximately 50% of recruits will have clinically significant dysphagia/aspiration, a correlation of approximately 0.3 between SIS and HRCA, and an area under ROC curve of  $c=0.600$  for SIS alone, with the proposed sample size, we will have 80% power to detect an increase in area under ROC curve as small as 0.240 at  $\alpha=0.05$  with one of the 3 strategies that involve HRCA [134, 135].

**Project coordination and management:** [name] will direct the study and will lead the analysis and algorithm

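### Aim 3 sets goals for both OPD and aspiration, but A3.e compares SIS with HRCA only on a merged OPD/aspiration outcome, so a significant result would not show better detection of aspiration

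*Combined protocol and SAP*

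**What the plan says.** **Goals.** The title of Aim 3 names both dysphagia and aspiration. A3.a says the device must do better than SIS at finding patients at risk of silent aspiration and of clinically significant dysphagia. A3.f makes accurate identification of patients at risk of silent aspiration the benchmark for success.

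**Analysis.** A3.e fits logistic models "with presence/absence of clinically significant OPD/aspiration as the dichotomous dependent variable" and compares c-statistics by DeLong's method. It specifies no comparison on aspiration alone. On the reference side, A3.d STEP 5 states: "The MBSImP, the PAS and the Normalized Residue Ratio Scale will be used to measure swallow impairment, airway protection and post-swallow pharyngeal residue". No cutoff is given, and no rule for combining the three measures.

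**What SIS is for.** The descriptions differ:
- An aspiration screen: in Significance, SIS "relies on whether the patient coughs or chokes during or after swallowing to predict aspiration (Figure 3"; Table 3 in A3.b is titled "Sensitivity and specificity of screening protocols for aspiration".
- An OPD screen: in Specific Aims, "Standard institutional screening (SIS) protocols are therefore used to predict OPD"; in Significance, observers are "observing for signs of OPD using standard procedures (Figure 2"; in A3.d STEP 3, staff score the Aim 3 screens by "denoting any signs of OPD or penetration/aspiration (e.g., wet voice, coughs) for each swallow that is observed". A3.b likewise expects screening to detect OPD.

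**What HRCA is built on.** Aim 2 equates HRCA signals to MBSImP, PAS and pharyngeal residue, and A3.d STEP 3 takes the HRCA output from Aims 1 and 2.

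**The concern.** A patient with residue or impaired physiology but no airway invasion may be positive on the merged outcome and negative on an aspiration outcome. If that patient does not cough, SIS is wrong on the first target and right on the second. If the patient does cough, SIS is right on the first and wrong on the second. HRCA is developed on every dimension of the reference standard. SIS, as partly described, responds to signs of aspiration.

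With only the merged comparison, a significant difference in c could arise entirely among patients without airway invasion. The trial would then have met its statistical criterion without answering the silent-aspiration question that A3.a and A3.f pose.

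**Working it through.** **1. The plan's own power figure.** Inputs from A3.h: 46 effective patients, 50% positive (23/23), SIS c = 0.600, increase 0.240 (to 0.840), correlation 0.3, α = 0.05, taken here as two-sided. I used Hanley-McNeil variances, with n1 positives and n0 negatives:

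V(c) = [c(1-c) + (n1-1)(Q1-c²) + (n0-1)(Q2-c²)]/(n1·n0), where Q1 = c/(2-c) and Q2 = 2c²/(1+c).

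V(0.60) = 0.00705 and V(0.84) = 0.00358. SE = √(V1 + V2 - 2·0.3·√(V1·V2)) = 0.0872. Power = Φ(0.240/0.0872 - 1.96) = 78.5%, and the detectable increase at 80% power is 0.244. The stated 80% and 0.240 are reproduced closely, so the power figure is not in question.

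**2. How the target moves the SIS c-statistic.** For a pass/fail screen, c = (sensitivity + specificity)/2. Let p = 0.5 be the share positive on the merged outcome, a the share of those with airway invasion, s the SIS fail rate with airway invasion, g the fail rate in positives without it, and h the fail rate in patients with neither.

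- Merged target: c = [a·s + (1-a)·g + 1 - h]/2
- Aspiration target: c = [s + 1 - FP]/2, where FP = [p(1-a)·g + (1-p)·h]/(1 - p·a)

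The documents give neither a nor g. As an illustration, take the 92%/66% screen in Table 3 (s = 0.92, h = 0.34) and assume a = 0.5, so FP = (g + 2h)/3:

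| g (assumed) | c, aspiration target | c, merged target | change |
|---|---|---|---|
| 0.34 | 0.790 | 0.645 | -0.145 |
| 0.63 | 0.742 | 0.718 | -0.024 |
| 0.92 | 0.693 | 0.790 | +0.097 |

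The two targets give equal c at g = 0.69. For the 100%/50% screen with a = 0.5, the change runs from -0.125 to +0.083, with break-even at g = 0.80.

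This takes Table 3 specificity as specificity in patients without OPD. If it is instead held fixed over all non-aspirators, break-even falls at 0.63 and 0.75 for the two screens. The sign still depends on g. Specific Aims says only that up to 60% of non-aspirators cough during SIS, which is a ceiling and is not split by OPD status.

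**3. What an airway-invasion comparison could detect.** The Table 4 pilot had 13 of 40 patients with impaired safety. Applied as an assumption, 46 × 13/40 = 14.95, or about 15 positive and 31 negative. Then V(0.60) = 0.00839, V(0.84) = 0.00481 and SE = 0.0969.

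- Power for 0.60 versus 0.84: Φ(0.240/0.0969 - 1.96) = 70%
- Detectable increase from 0.60 at 80% power: 0.266

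Table 3 implies higher SIS values for aspiration: (1.00 + 0.29)/2 = 0.645, (0.92 + 0.66)/2 = 0.79, (1.00 + 0.50)/2 = 0.75, and 0.72 to 0.82 for the fourth screen. With SIS at 0.75 and HRCA at 0.84, power is 17% at 15/31 and 21% at 23/23.

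**The case against.** **OPD is a target the plan assigns to SIS.** Specific Aims, Significance, A3.b and the Aim 3 scoring step all say so, and the Aim 3 hypothesis is about detecting OPD and non-OPD. OPD that a cough-based screen misses is the gap the trial means to close. This stands, and it is why the merged outcome should remain the main one.

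**A reader might infer that the merged target handicaps SIS by design.** The documents do not support that. The direction turns on g, which is unknown, and SIS gains if enough non-aspirating OPD patients fail it. Joining the 50% of A3.h to the pilot's 13/40 would suggest that 1 - 0.325/0.50 = 35% of positives have no airway entry, but that combines an assumed prevalence in future patients with a different pilot cohort.

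**The assumed SIS c of 0.600 lies below every value implied by Table 3, and the plan does not explain why.** That is not proof of dilution. The plan's own text on silent aspirators (half do not choke) and coughing non-aspirators (up to 60%) would imply a c as low as (0.50 + 0.40)/2 = 0.45.

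**HRCA's advantage on MBSImP or residue is possible but not shown.** The airway-protection accuracy in A3.c and Table 4 is for swallowing safety.

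**Conclusion.** The point holds in this form: Aim 3 states an aspiration goal that its only specified comparison cannot answer. The target can move the SIS c-statistic by amounts that matter beside the 0.240 design increase. The range was -0.145 to +0.097 in the illustration, which assumes half of the positives have airway invasion and uses one Table 3 screen. Neither the sign nor the size in this trial can be predicted from the documents.

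A reader might go further and require HRCA to win on PAS before any superiority over SIS is claimed. That would replace the stated OPD hypothesis, and at 46 patients it would be hard to meet: 17% power if SIS is at 0.75 and HRCA at 0.84. A claim about OPD can rest on the merged outcome; a claim about aspiration cannot.

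**What to change.** In A3.e:
- Keep OPD/aspiration as the main outcome.
- Add a prespecified secondary SIS-versus-HRCA comparison with airway invasion on VF as the dependent variable, defined as PAS 3-8, the abnormal range used in A2.c.
- Report the two results separately, and limit any conclusion about aspiration to the PAS comparison. Describe it as airway invasion, because A3.c shows that this range includes penetration above the vocal cords.

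The PAS scores are already collected in A3.d STEP 5, so the added work is one further set of models. The cost is precision. At about 15 positives of 46, the detectable increase from c = 0.60 is about 0.27, power for 0.60 versus 0.84 is about 70%, and power is much lower if SIS performs near its Table 3 values. The secondary result should therefore be presented as an estimated difference with a confidence interval, and a non-significant result should not be read as evidence of equal accuracy.
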